**FHCC Patients: Emergency (24-hour) [contact]; [contact]**

**24-Hour [contact] (Ask for the Infectious Disease fellow On-Call)**

**UW Medical Center Patients: Paging Operator [contact] and ask for [name]**

## PROTOCOL SYNOPSIS

Protocol Number: 10691	Product Names: VIR-7831 (Sotrovimab)
Title of Study: Pharmacokinetics of a SARS-CoV-2 Monoclonal Antibody in Hematopoietic Stem Cell Transplant Recipients	
PI: [name]	
Sponsor-Investigator: [name]	Phase of Development: Phase 1
Study Objectives: To assess the pharmacokinetics of the anti-SARS-CoV-2 monoclonal antibody (mAb) VIR-7831 up to six months post-transplant in hematopoietic stem cell transplant (HCT) recipients.	
Primary: To determine the levels of VIR-7831 mAb post-transplant in serum over time.	
Secondary: 

1. To compare the half-life of VIR-7831 in autologous vs. allogeneic transplant, cord vs. non-cord allogeneic transplant, matched vs mis-matched donors, in patients with and without GVHD, and in patients with and without diarrhea

2. To monitor the frequency of breakthrough SARS-CoV-2 acquisition in HCT recipients who have received VIR-7831

3. To compare antibody levels from serum collected by venipuncture versus self-collected using a TASSO device.

4. To monitor the development of anti-drug antibodies

5. To monitor safety with routine labs as part of standard post-transplant care.

6. Exploratory: To measure VIR-7831 and SARS-CoV-2 neutralizing antibodies in nasal swabs and SARS-CoV-2 neutralizing antibodies in serum.

	
Study Purpose and Rationale: 
Respiratory viral infections cause significant mortality, morbidity, and health care costs in the immunocompromised HCT population. The current pandemic caused by the novel coronavirus SARS-CoV-2 poses a threat to this vulnerable population. HCT recipients are most vulnerable to infection during the early post-transplant period; however, vaccination is also thought to be ineffective during this period because the immune system is not yet fully reconstituted. Current guidelines recommend considering vaccination at least three months after transplant even though efficacy may be sub-optimal. Monoclonal antibodies (mAbs) against SARS-CoV-2 administered pre-transplant represent a strategy to reduce the risk of COVID-19 among HCT recipients. Several mAb candidates against SARS-CoV-2 are advancing through clinical trials. VIR-7831 is an extended half-life mAb was granted Emergency Use Authorization by the Food and Drug Administration (FDA) in May 2021 for early treatment, based on the recently completed phase 3 COMET-ICE clinical trial (NCT04545060) demonstrating an 85% reduction in hospitalization or death when VIR-7831 was given early after infection as monotherapy.
 
This study seeks to define the pharmacokinetics of VIR-7831 against SARS-CoV-2 with regards to half-life in the serum and the impact of HLA-mismatch and GVHD on these kinetics in transplant recipients. Evidence exists in the literature suggesting that the half-life of CMV- and RSV-specific antibodies is significantly shortened in HCT recipients, and particularly in those who received an allogeneic transplant. One possible explanation for this phenomenon is accelerated antibody loss through GVHD-related gut leakage. A better understanding of the kinetics of antibody decay in the serum could help determine the utility of immunoprophylaxis in bridging this window of vulnerability.
	
Study Population: 
This is a prospective, open-label, single arm study that will enroll a target of 50 subjects prior to HCT. We will enroll patients who are pre-transplant and have completed a transplant arrival visit and who meet other eligibility criteria (detailed below). Participants will receive one 2,000 mg dose intravenously of VIR-7831 within one week (seven days) prior to the start of conditioning, and the mAb will be infused at least 24 hours prior to the start of conditioning, i.e. mAb infusion will occur within 1-7 days prior to conditioning).
	
Patient Inclusion Criteria: 

• Age at least 18 years of age

• Undergoing HCT (any donor or stem cell source, including autologous or cord blood transplant)

	

- History of prior transplants is permitted
- History of COVID-19, positive PCR of a respiratory specimen for SARS-CoV-2 as long as it is not within four weeks from conditioning, or seropositivity for SARS-CoV-2 is permitted
- History of SARS-CoV-2 infection or vaccination of the donor are permitted.
- Able to provide informed consent
- Post-enrollment vaccination is anticipated and permitted
- Administration of IVIG before or during the study is permitted

**Patient Exclusion Criteria:**

- Positive PCR result for SARS-CoV-2 within four weeks of scheduled conditioning
- Signs or symptoms of uncontrolled active infection
- Pregnant or breastfeeding
  - Pregnancy test is obtained as part of pre-transplant evaluation in women of child-bearing potential at arrival to transplant and again within 7 days of conditioning and will be confirmed as negative by review of the chart
- Previous known allergies to any component of VIR-7831
- Previous anaphylaxis or severe hypersensitivity reaction, including angioedema, to a mAb
- Participants of other clinical studies that preclude the use of other investigational compounds
- Participants who, in the judgment of the investigator, will be unlikely or unable to comply with the requirements of the protocol or unlikely to survive to the end of study

**Test Product, Dose, and Mode of Administration:**

**Product:** VIR-7831

**Dose:** 2,000 mg mAb

**Mode of Administration:** Intravenous infusion over approximately 60 minutes.

**Timing of Administration:** Within one week prior to the start of conditioning.

VIR-7831 is a fully human immunoglobulin G1 kappa (IgG1κ) mAb derived from the parental mAb S309, a potent neutralizing mAb directed against the spike protein of SARS-CoV-2. S309 binds to a highly conserved epitope of the SARS-CoV and SARS-CoV-2 spike protein receptor binding domain (RBD) and inhibits SARS-CoV-2 infection in vitro. The Fc region of the molecule contains the 2 amino acid Fc-modification LS, designed to provide extended half-life and enhanced biodistribution to the lung. VIR-7831 is provided as a sterile liquid for intravenous infusion or intramuscular injection. All clinical study materials are manufactured in accordance with current Good Manufacturing Practice (cGMP) regulations. VIR-7831 has been tested in the phase 3 COMET-ICE clinical trial and reduced hospitalization and death when used as early treatment for COVID-19.

**Clinical Observations and Safety Assessments.** Clinical evaluation will occur immediately prior to mAb administration. Participants will complete a weekly symptom questionnaire prior to and weekly after mAb administration for a total 24 weeks. Safety assessments will be performed with routine labs as part of standard stem cell transplant care.

**Biomarker Assessments:** Immediately prior to mAb administration and at the end-of-infusion, weekly up to week 4, monthly up to week 12, and at week 24 after mAb administration, blood will be drawn by venipuncture (10-20 mL per blood draw) by nursing, a phlebotomist, or trained study staff. At week 12, and monthly thereafter to the end of primary end-point (week 24), blood is self-collected using a TASSO device and by venous blood draw. Nasal specimens will be collected by mid-nasal foam swab at the same time-points as blood draws. Nasal swabs and blood via TASSO (or venous blood draw) will also be collected off-schedule for SARS-CoV-2 PCR and antibody testing as needed based on respiratory symptoms (answering yes to one or more of the nose or chest symptoms) within 48 hours of symptom of symptom onset, up to week 36. If positive for SARS-CoV-2, weekly nasal swabs will be obtained longitudinally for SARS-CoV-2 PCR until negative or until week 36. Serum, plasma, or nasal swabs will be processed and stored at either 4°C, at -20°C, or at -70°C until use, as appropriate. Testing will include serum and nasal total IgG, VIR-7831, SARS-CoV-2-specific IgG, SARS-CoV-2 neutralization titers, and anti-drug antibodies. Testing will be performed at the Fred Hutch, UW, or by Vir Biotechnology.

**Statistical Methods:**

The target enrollment for this trial is 50 pre-hematopoietic stem cell transplant candidates. Twenty subjects have already been infused with a 500 mg dose. Thirty additional subjects will be infused with the 2,000 mg dose. Descriptive statistics will be used to analyze the data. An exponential decay model will be used to calculate half-life.

**Sample size and estimated duration of the study:** Based on the estimated number of treated patients meeting primary eligibility criteria per year and an estimated 35% consent rate, it will be feasible to enroll approximately 55 subjects over 6-12 months. Our final anticipated sample size will be 50 subjects after accounting for an estimated 10% dropout rate prior to completing 24 weeks of follow-up. Ten of these subjects will be autologous HCT candidates. Forty will be allogeneic HCT candidates, of which five will be cord blood HCT candidates. Given our sample size, we will be able to estimate a half-life for VIR-7831.

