## 12.2 Secondary Objectives

- Secondary and exploratory objectives: We will compare antibody levels in autologous vs. allogeneic transplant, cord vs. non-cord allogeneic transplant, matched vs. mismatched transplants, in patients with and without GVHD, and in patients with and without diarrhea to test if HLA-mismatching, GVHD, and/or diarrhea are associated with accelerated antibody decay. Diarrhea will be assessed on the weekly questionnaire and the presence/severity/tissue involvement of GVHD will be assessed by review of the medical record at all timepoints indicated in Figure 1. We will also compare antibody levels from serum collected by venipuncture versus self-collected using a TASSO device and from fluid collected by nasal swabs. Based on preliminary and published data, we expect a high concordance between antibody levels from capillary blood collected by TASSO and venous blood collected by venipuncture or from a central venous catheter. If there is a slight discrepancy, we can calculate a correction factor based on the results from the paired specimens collected on week 12. If there is an unexpected significant discrepancy between antibody levels that cannot be corrected, we will have a venous blood draw at week 24 to calculate half-life using just venous blood samples. We will monitor for breakthrough SARS-CoV-2 infection by PCR of fluid collected by nasal swabs. If breakthrough infection does occur, we may sequence the spike gene (or entire viral genome) to determine the variant and identify possible resistance mutations. We will also measure anti-drug antibodies in case this is correlated with half-life. We will also monitor routine safety labs as part of standard post-transplant care. Comparisons will be tested using a t-test. As part of an exploratory analysis, we may also calculate the half-life of VIR-7831 and of SARS-CoV-2 neutralizing antibodies in nasal swabs and of SARS-CoV-2 neutralizing antibodies in serum after infusion of VIR-7831.

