## 12.3 Sample Size and Accrual

At the Fred Hutch, we perform approximately 250 allogeneic transplants per year, approximately 5% of which involve umbilical cord blood donors. We also perform approximately 180 autologous transplants per year. The target enrollment for this trial is approximately 50 HCT candidates, of which ten participants will be autologous HCT candidates and 40 will be allogeneic HCT candidates (including cord blood HCT candidates). At least 8 of the allogeneic HCT candidates will be from HLA-mismatched (related or unrelated) HCT recipients. Based on the estimated number of treated patients per year (and previously treated patients since 2013), as well as the estimated number of patients that we may enroll (i.e., ‘feasible’ patients) after accounting for estimated eligibility and consent rates, it will be feasible to enroll approximately 55 subjects over 6-12 months. Our final estimated sample size will be 50 subjects after accounting for an estimated 10% dropout prior to completion of the full 24-week study period. If the dropout rate is higher at three months after mAb infusion, we may enroll more patients to achieve a target of 50 overall subjects. The study is open to anyone regardless of gender or ethnicity. Efforts will be made to extend the accrual to a representative population. If accrual is slow, we may add another site. If accrual of the HLA-mismatched strata is slow, we may analyze and report the results in the HLA-matched strata once that is fully enrolled given the urgency of the pandemic.

- Primary objective: Our primary endpoint is to calculate the half-life of VIR-7831 post-transplant. Based on the half-life seen with other antibodies containing the LS mutation in adults who have not undergone transplant, we anticipate a half-life of up to 3 months. However, this half-life may be shortened in transplant recipients. Since we will use descriptive statistics, the sample size is

sufficient to provide data to calculate the half-life. Levels of VIR-7831 can be measured using an idiotypic antibody assay that is not affected by COVID-19 infection or vaccination.

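### The synopsis counts on five cord-blood recipients, but the plan's own accrual inputs lead to an expectation of about two (about four in the best case), and the cord versus non-cord comparison is still to be t-tested

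*Combined protocol and SAP*

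**What the plan says.** The Protocol Synopsis, under sample size and estimated duration, describes the final sample: "Our final anticipated sample size will be 50 subjects after accounting for an estimated 10% dropout rate prior to completing 24 weeks of follow-up". It then splits those 50 into ten autologous and 40 allogeneic subjects, and adds: "Forty will be allogeneic HCT candidates, of which five will be cord blood HCT candidates". The accrual basis is "an estimated 35% consent rate" and the statement that "it will be feasible to enroll approximately 55 subjects over 6-12 months".

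Section 12.3 gives the site volume: "we perform approximately 250 allogeneic transplants per year, approximately 5% of which involve umbilical cord blood donors". For the other stratum it says: "We also perform approximately 180 autologous transplants per year". It repeats the 10 and 40 split and counts cord recipients within the 40, but gives no cord number. It sets a minimum of 8 for HLA-mismatched recipients and none for cord.

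Cord versus non-cord half-life is part of secondary objective 1 (Section 3.2). Section 12.2 lists the comparison with the others and says: "Comparisons will be tested using a t-test". No significance level, power, detectable difference or minimum group size is given.

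**The concern.** Five of 40 is 12.5%, which is 2.5 times the 5% cord share given in Section 12.3, and nothing in the plan explains the difference. The two sections describe the same 40 patients, so the stated subgroup should follow from the stated volume, consent rate and accrual period, or from a quota.

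What is at stake is one named secondary comparison. If the cord group is very small, the planned test either cannot be run or rests on almost no information about variation among cord recipients. A non-significant result could then be taken as evidence that cord source makes no difference. Section 12.3 labels the HLA-mismatch comparison as pilot data but gives the cord comparison no such caveat.

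**Working it through.** **Inputs.** Synopsis: 5 cord of 40 allogeneic; 35% consent; about 55 enrolled in 6 to 12 months; 10% dropout; final sample 50. Section 12.3: about 250 allogeneic transplants a year, about 5% cord; about 180 autologous a year.

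**Step 1. The plan's total reproduces.** 50 / (1 − 0.10) = 55.6, against about 55 stated. The overall accrual figure is not in question.

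**Step 2. Cord count if cord patients enter in proportion to volume.**
- Among 40: 40 × 0.05 = 2.0.
- Among about 44 enrolled before dropout (40 / 0.90 = 44.4): 44 × 0.05 = 2.2.
- Cross-check: consenting allogeneic patients number 250 × 0.35 = 87.5 a year. Enrolling 44 takes about half of them (44 / 87.5 = 0.50), and half of the 4.4 consenting cord patients (Step 3) is again 2.2.

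With X distributed as Binomial(40, 0.05):
- P(X = 0) = 0.95^40 = 0.129
- P(X = 1) = 40 × 0.05 × 0.95^39 = 0.271
- P(X ≤ 1) = 0.40
- P(X ≥ 5) = 0.048 (0.067 with n = 44)
- 95% range: 0 to 5

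**Step 3. Cord count if every cord candidate is eligible and approached.**
- Cord transplants: 250 × 0.05 = 12.5 a year.
- Consenting: 12.5 × 0.35 = 4.375 in 12 months, 2.19 in 6 months.
- Completers after 10% dropout: 4.375 × 0.90 = 3.94 in 12 months, 2.19 × 0.90 = 1.97 in 6 months.
- Chance of five or more enrolled in 12 months: 42% from Binomial(12, 0.35), 50% from Binomial(13, 0.35), 44% from Poisson(4.375).
- Chance of five or more completers in 12 months: about 36%, from Poisson(3.94).
- Expected time to five enrolled: 5 / 4.375 × 12 = 13.7 months. To five completers: 13.7 / 0.90 = 15.2 months. Both exceed the stated 6 to 12 months.

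**Step 4. What the comparison could show.** The documents give no between-subject SD for half-life. I assume a log-scale SD of 0.34 and show the range 0.25 to 0.45. The ratio of half-lives detectable with 80% power at two-sided 5% is exp[−(t₀.₉₇₅ + t₀.₈₀) × SD × √(1/n₁ + 1/n₂)] on 38 degrees of freedom, where the two t values sum to about 2.875.

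| Cord vs non-cord | √(1/n₁ + 1/n₂) | Detectable shortening, SD 0.34 (0.25 to 0.45) |
|---|---|---|
| 5 vs 35 | 0.478 | 37% (29% to 46%) |
| 2 vs 38 | 0.725 | 51% (41% to 61%) |

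With no cord recipients there is no comparison. With one, the cord group has no variance of its own: an unequal-variance t-test cannot be computed, and a pooled test takes its variance wholly from the non-cord group.

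**The case against.** The strongest reply is that enrolment is not proportional to volume. The site performs 180 autologous to 250 allogeneic transplants, yet the plan takes 10 and 40, and HLA-mismatched recipients have a floor. Composition is thus set by stratum. The consenting allogeneic pool is about twice what is needed, so cord candidates could be favoured. Section 12.3 also allows a further site if accrual is slow and extra enrolment if dropout is high. This stands as far as it goes: the 5% chance of reaching five applies only if cord candidates are not favoured. But those provisions are general. None is directed at cord, and the one stratum-specific fallback concerns HLA mismatch.

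A reader might infer that 4.4 is a ceiling and that five cannot be reached. The documents do not support that. The figure is an expected value, and in the best case five or more are enrolled with a probability of 42% to 50%. With every input given as approximate, five is not incompatible with that best case.

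A reader might also infer that the t-test loses a stated size or power. None is stated. Five is an accrual figure that appears only in the synopsis, and the synopsis says that descriptive statistics will be used. Moreover, even 5 versus 35 would detect only a large difference, so the limited value of the test does not come only from the miscount. That is a further reason to make the comparison descriptive.

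**Conclusion.** The point holds in this form: the synopsis states five cord recipients without qualification, while the plan's own inputs give an expectation of about 2 under proportional accrual and 2.2 to 4.4 enrolled (2.0 to 3.9 completers) if every cord candidate is eligible and approached for 6 to 12 months. Even the most favourable expectation is below five. Without targeted cord accrual five is unlikely, though not impossible, and there is about a 40% chance under proportional accrual that the t-test has none or one in the cord group.

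This rests on the 35% consent rate applying equally to cord candidates and, for the upper figures, on full eligibility, since the documents give no eligibility rate. The documents also do not say how many of the 20 participants already infused are cord recipients; that count would update the expectation. The detectable differences depend on the assumed SD. The effect is confined to one secondary comparison.

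**What to change.** - In the synopsis and Section 12.3, replace the flat figure of five with the same statement in both places: about 2 cord recipients expected, and about 4 if every cord candidate is approached over a full 12 months.
- In Section 12.2, take cord versus non-cord out of the t-tested comparisons. Report each cord recipient's half-life beside the non-cord distribution, and state that no inference is drawn.
- If the sponsor prefers to keep five, Section 12.3 needs an explicit cord accrual target and the means and time to reach it. The comparison would still be sensitive only to large differences.

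The cost of the recommended change is a few sentences. The stated cord figure becomes less favourable and one formal test is lost. No extra patients are needed, and the primary objective and total sample size stay as they are.

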## 1. BACKGROUND

Respiratory infections after hematopoietic cell transplantation (HCT) lead to significant morbidity, mortality, and health care costs. Early after transplantation, HCT patients have incomplete humoral immunity, making them extremely vulnerable to infections. Up to a third of HCT recipients acquire a respiratory viral infection within six months of transplant(1-7). In up to a third of those patients, the virus progresses from the upper to the lower respiratory tract (LRT)(2, 5). Once the virus gains a foothold in the lower tract, little can be done for most viruses beyond supportive care. As a result, up to 40% of patients with lower tract disease die within three months. The newly emerged COVID-19 pandemic caused by SARS-CoV-2 poses a threat to HCT recipients and development of COVID-19 post-transplant is associated with poor overall survival(8-10). This virus has spread throughout the world at an alarming pace, leading to over 150 million cases and 3.1 million deaths as of April 30, 2021 (Johns Hopkins COVID-19 dashboard).

mAbs can be used to prevent disease in vulnerable populations when given as prophylaxis. For example, the mAb palivizumab is approved as prophylaxis against pneumonia caused by respiratory syncytial virus and is administered to high-risk infants. Protective mAbs against SARS-CoV-2 are urgently being developed, but their role in providing long-term protection in the setting of HCT remains to be determined. mAbs against SARS-CoV-2 administered pre-transplant or early post-transplant represent a strategy to reduce the risk of COVID-19 among HCT recipients. Vir Biotechnology, Inc. (Vir) has developed a fully human neutralizing anti-SARS-CoV-2 antibody, VIR-7831 (GSK4182136), which contains a 2 amino acid Fc-modification ("LS") that is designed to improve bioavailability in the respiratory mucosa and increase half-life(11-13). VIR-7831 binds to a conserved epitope on the SARS-CoV and SARS-CoV-2 spike protein and has been shown to neutralize pseudovirus and live virus in several independent laboratories(14). VIR-7831 was granted Emergency Use Authorization by the Food and Drug Administration (FDA) in May 2021 for early treatment based on the interim analysis of the Phase 3 COMET-ICE clinical trial (NCT04545060). The COMET-ICE study population included adults with mild or moderate COVID-19 who were at high risk for progression to severe disease. On March 10, 2021, an independent data monitoring committee recommended that the trial be stopped for enrollment due to evidence of profound efficacy, demonstrating an 85% reduction in hospitalization or death when VIR-7831 was given early after infection as monotherapy. The multi-center, double-blind, placebo-controlled Phase 3 trial assessed the safety and efficacy of a single intravenous infusion of VIR-7831 (500 mg) or placebo in non-hospitalized participants globally, and this interim analysis included 291 patients in the treatment arm and 292 patients in the placebo arm. The primary efficacy endpoint was the proportion of patients who had progression of COVID-19 as defined by the need for hospitalization for at least 24 hours or death within 29 days of randomization.

The 500 mg dose of VIR-7831 has reduced *in vitro* neutralization potency against the Omicron BA.2 subvariant which has emerged as the predominant variant of SARS-CoV-2 in the United States. However, VIR-7831 retains protective efficacy *in vivo* due to its Fc effector functions(15). An increased dose of 2,000 mg is being proposed for the remainder of participants enrolled in this study to increase the expected duration of coverage given the current BA.2 predominant environment. Based on pseudotype and live virus neutralization data and pharmacokinetics (PK) data from multiple clinical studies evaluating the 500 mg dose, a preliminary population PK model was developed using data across several studies including COMET-TAIL, COMET-ICE, COMET-PEAK, BLAZE-4 and a PK study in individuals of Japanese and Caucasian descent. The predicted median (10th, 90th percentile) serum concentrations of sotrovimab at week 12 following a single 2000 mg IV dose is 84.3 (52.8,126.7) µg/mL. When assuming a lung:serum

ratio of 25%, a 2000 mg IV dose is expected to provide coverage against BA.1, BA.2 and BA.3 with serum concentrations achieving 13x, 1.4x and 5.6x lung tissue adjusted EC90 in 90% of patients at Week 12, respectively. When assuming a more conservative lung:serum ratio of 10%, a 2000 mg IV dose is expected to maintain serum levels at or above 5.3x, 0.56x, 2.23x lung tissue adjusted EC90 at Week 12 in 90% of patients for BA.1, BA.2 and BA.3 variants, respectively. Under the 10% and 25% lung:serum ratio assumptions, concentrations of sotrovimab at week 12 following a 2000 mg IV dose are expected to provide adequate protection in  $\geq 90\%$  of patients against variants that confer up to 20-fold and 49-fold shift in EC90 compared to WT, respectively. Similarly, this dose of sotrovimab at week 12 is expected to achieve adequate coverage for  $\geq 50\%$  of patients against variants that confer up to 31- and 78-fold shift in EC90 compared to WT when lung:serum ration are assumed to be 10% and 25%, respectively.

The normal serum half-life of immunoglobulin G (IgG) is approximately 21 days and is regulated by a balance of FcRn-mediated endocytosis and recycling versus endosomal degradation. To provide a product that has the potential to address multiple urgent medical needs including treatment, post-exposure prophylaxis (PEP) and pre-exposure prophylaxis (PrEP), a molecule with extended half-life is preferred. The well-characterized LS modification (M428L and N435S) increases immunoglobulin G1 (IgG1) binding to FcRn only at the acidic pH of the endosomal compartment, thereby increasing recycling of IgG back into the circulation(11-13). Notably, the LS mutations do not affect binding to FcγRs or complement and thus do not impair Fc-mediated effector functions. Transcytosis of IgG across mucosal surfaces including respiratory epithelium has been shown to be FcRn dependent(16, 17), thus the LS modification allows for less frequent dosing, an important characteristic for a product intended to be used in the prophylaxis setting. Moreover, this characteristic of the LS modification may increase respiratory mucosal distribution, an important consideration in respiratory diseases.

The LS mutation has previously been studied in humans in the context of a mAb targeting the CD4 binding site of the HIV-1 envelope glycoprotein (VRC01LS; NCT0259989, NCT02797171). VRC01LS was reported to be safe and well tolerated at doses of 5 to 40 mg/kg IV and at 5 mg/kg subcutaneous in healthy volunteers(13). PK analysis showed a half-life of 71 days, more than 4-fold longer than that seen previously with the parental wild-type molecule. No anti-drug antibodies (ADAs) were detected out to 48 weeks(13). This molecule continues in clinical development for treatment of HIV infection in adults and children (NCT02256631, NCT03707977). Similarly, VIR-2482, a neutralizing mAb against influenza A, demonstrated a longer terminal elimination half-life (mean: approximately 27 days) compared to the wild-type molecule (mean: approximately 13 days) in cynomolgus monkeys. VIR-2482 is now in a phase 1/2 clinical study (NCT04033406) and has been administered to healthy volunteers at doses up to 1800 mg. Preliminary data indicate the compound has been generally well tolerated with no significant safety issues identified, including in a phase 2/3 clinical study (NCT04545060) of 583 patients. Based on available data, the preliminary half-life estimate for VIR-2482 is approximately 58 days in humans.

